Potential participants will be recruited from VA clinics (including primary care and mental health) and the community, following procedures that have been proven successful in our previous meditation and yoga trials. The initial contact for potential participants will be with a study recruiter/assessor, who will complete informed consent and conduct the evaluation for eligibility (see *Assessment*). After eligibility and consent are confirmed, the participant will complete the baseline assessment and then will have brief safety assessments every class; they will be asked to complete a total of 12 classes within 14 weeks. A follow-up will occur 12 weeks after the completion of the final class. No shows will receive a telephone follow-up. Participants will receive a payment for each assessment session (\$50 baseline part 1, \$50 baseline part 2, \$50 post-treatment part 1, \$50 post-treatment part 2, \$50 follow-up part 1, \$50 follow-up part 2 for a total of \$300; refer to Table 1).

Randomization will be done by the study statistician. In the initial phase of the trial, this was a 2:1 allocation to yoga and physical activity and took place at the individual level. Uneven allocation was planned to allow for sufficient power to accomplish the modeling proposed in Aim 2 (refer to *Sample Size*); given pandemic-related difficulties with accrual, however, the allocation will be reversed to 1:3 for the final months of the study to accomplish a minimum of 48/cell. The randomization table will be prepared prior to start of the study and revised for the new allocation strategy. Using an individual randomization strategy and continual group enrollment allows patients to begin treatment more quickly (i.e., as soon as the baseline evaluation is complete), which reduces attrition. This continual enrollment strategy is possible because the yoga and physical activity classes do not build from week to week; rather, every class provides multiple options for each pose/exercise to allow for individual differences, as is consistent with typical practice in the community. Further, sharing of personal information is minimized in this type of class, so newcomers are unlikely to cause discomfort among group members. Further, this strategy may support better retention. By allowing participants 14 weeks in which to complete 12 classes, participants will be able to make up missed classes to receive the full “dose.”

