Clinical outcomes. The **Clinician Administered PTSD Scale (CAPS-5)**; Weathers, Blake, et al., 2013) will be used to establish the PTSD diagnosis and quantify severity. This clinician-rated measure of PTSD is the “gold standard” for assessing PTSD and takes 45-60 minutes to complete. The CAPS has high internal consistency (for the DSM-IV version, alphas of 0.87 and 0.88 for the three PTSD symptom clusters and 0.95 for PTSD symptoms overall) and validity (sensitivity, specificity, efficiency, and agreement). The CAPS total score will be used as the primary measure of clinical outcome. Given our interest in exploring the effect of these interventions on symptoms that commonly co-occur with PTSD, we will also assess depression severity as measured by the 20-item **Center for Epidemiologic Studies Depression Scale Revised (CESD-R)**; Eaton, Muntaner, Smith, Tien, & Ybarra, 2004), general anxiety as measured by the 40-item **State-Trait Anxiety Inventory (STAI)**; Spielberger, Gorsuch, Lushene, Vagg, & Jacobs, 1983), anger as measured by the 35-item **State-Trait Anger Expression Inventory – II (STAXI-II)**; Spielberger, 1991) and sleep problems as measured by the 7-item **Insomnia Severity Index (ISI)**; Bastien, Vallieres, & Morin, 2001), a 7-item instrument that assesses the consequences of and distress related to insomnia, will be included as well. Finally, the **Sheehan Disability Scale (SDS)**; Sheehan, Harnett-Sheehan, & Raj, 1996), a 3-item measure of impairment in work, social and family settings, will be included. This widely-used but low-burden measure of disability has been shown to change with treatment in similar population samples (e.g., [name], Schnurr, et al., 2016).

Clinical utility. Clinical utility can be defined as the usefulness of an intervention in clinical practice and is considered to have four major dimensions (Smart, 2006). The **appropriateness** of yoga for PTSD depends on its efficacy (addressed in Aim 1) but also on the successful integration of the intervention into current care practices. **Accessibility** involves the factors involved in making yoga available to Veterans. Issues such as the usability of the manual and the way in which training can be conducted speak to **practicality**. Finally, the **acceptability** of yoga depends on its reception by key stakeholders, including Veterans and clinicians. Aspects

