Each outcome variable will be graphed versus time for each subject for all available time points (baseline, mid-treatment, post-treatment, follow-up) to evaluate what function of time best describes the data. Hypotheses 1a and 1b will be tested using the Mixed Effect Model (Hedeker, Gibbons, & Waternaux, 1999). This method is robust with respect to drop-out and missing data. These mixed models allow us to assess whether important estimates are dependent on missing data patterns, and provide overall estimates of effects by averaging over the various missing-data patterns (Hedeker et al., 1999). In addition, we will use the extension of the Pattern-Mixture Models (Guo, Ratcliffe and Ten Have, 2004), which allows subject-to-subject heterogeneity and assess if there is bias due to drop out or missing data. The Mixed Effect method has several advantages over more traditional analytic approaches such as a change score, end-point or repeated measures analysis of variance. It allows the inclusion of subjects with missing data or those who were terminated early in the study, without relying on data imputation procedures. This method provides an estimate of the individual variability around the population trend, the variability of the individual intercepts (baseline values) and slopes (changes across time), and the correlation between them. We will include a random intercept, a random effect for assessment time, and fixed effects for comparison groups and group-by-time interaction in the model. A fully saturated treatment by time model will be utilized for inference. Co-variance structure will be chosen based on Akaike's Information Criterion (AIC). Random group level treatment effects will also be evaluated for importance based on the model AIC. This allows for any group level effects to be incorporated into the model. Denominator degrees of freedom will be calculated using the Kenward-Roger small sample correction. Statistical significance will be determined by $p < .05$ for hypothesis 1a and $p < .01$ (.05/5 to correct for multiple comparisons) for hypothesis 1b.

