remove variables or create composites. Correlation coefficients among the outcomes for each mediator will be examined. Furthermore, the main effect of each outcome will be examined in the mixed effect model. Low correlated outcomes or outcomes that are highly (greater than .8) correlated with each other and/or low contribution in the model will be considered to be dropped from the model. The effect of mediators in the model can be calculated based on either the difference between two regression parameters ($\tau - \tau^2$) or the multiplication of two regression parameters ($\alpha\beta$) (MacKinnon, Warsi, & Dwyer, 1995). The variance estimates produced by the various methods are quite similar to each other and to the true value of the variance in situations involving continuous multivariate normal data and a continuous independent variable (MacKinnon et al., 1995). Although there is some evidence that the least model in the case-control study design setting this approach could provide biased estimations for the indirect effects (Wang et al., 2012), we believe the Sobel (1982) procedure to test for significant mediation is most appropriate approach for this study. Next we will use the formula provided by MacKinnon and Dwyer (1993) to determine the percentage of the intervention condition to primary outcome path that was accounted for by change in our mediator. We acknowledge that this method may not be supportable given the need to reduce sample size. If the study biostatistician determines that this is the case, she will utilize other strategies to analyze available data and generate testable hypotheses for future studies. The exploratory aim will be analyzed using similar approach. Data will be analyzed from all randomized subjects on whom we have a baseline assessment and at least one post-baseline evaluation. All statistical tests will be two-tailed. We will adjust p-values for multiple testing as appropriate.

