Sample size. We used the method provided by Hedeker, Gibbons, & Waternaux (1999) for the Random Regression Model and the RMASS program provided by Hedeker (2016) to estimate needed sample size for Aim 1. Medium effect size was selected based on finding from previous yoga trials (Wells et al., 2016) and was defined as a between-group difference increasing linearly from 0 at baseline to .5 SD units at the last time point. The minimum power estimation is based on sample size calculation for 10% and 20% attrition, correlations of 0.2, 0.5, and 0.8 between the repeated measures, and for medium and large effect sizes. We are confident that with the proposed total sample size of at least 48/arm would be sufficient to achieve a minimum 80% power for the primary aim.

Management

Management of this single-site study will be [name] responsibility. She has considerable experience in research management from small developmental grants (e.g., NCCIH R34) to a large multi-site consortium (INTRuST PTSD/TBI Clinical Consortium Deputy Director) and center of excellence (VASDHS CESAMH Associate Director). Administrative aspects of the project will be supported by [name], who has been [name] lead coordinator for more than a decade. [name] will coordinate scientific aspects of the project, holding regular meetings with the investigative team. [name], the study biostatistician, will work closely with [name] around data management and analysis. [name] will draw on his experience with yoga research to help with issues of recruitment, enrollment and retention. Drs. [name] (attention) and [name] (pain) will provide guidance in their relative areas of expertise. [name], who is a licensed clinical psychologist, also will be responsible for clinical oversight. The timeline of major study activities is presented in Table 2.

Table 2. Study Timeline

Year 1 (2018-2019)	Year 2 (2019-2020)	Year 3 (2020-2021)	Year 4 (2021-2022)	Year 5 (2022-2023)
Original Timeline				

Set-up	Recruitment (approx. 6/month x 30 mos)	Follow-up, data lock	Dissemination	Analyses	
Regulatory	Assessment				
Hiring	Intervention delivery, fidelity (12 groups)				
Training	Data management				
Recruitment	DSMB reporting				
Revised Timeline					

 ✓ Set-up ✓ Regulatory 	
 Recruitment (approx. 6/month x 30 mos) Assessment Intervention delivery, fidelity (12 groups) Data management DSMB reporting 	Follow-up, data lock	Dissemination	Analyses	

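### The 80% power statement names no alpha or outcome; at the .01 threshold set for the five Aim 1b outcomes, power for the plan's medium effect is about 24–45% unless correlations are near .8

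*Combined protocol and SAP*

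**What the plan says.** The Sample size paragraph at the end of the Analytic Plan reports that a random-regression method and its companion program were used "to estimate needed sample size for Aim 1". The medium effect is a gap between arms that starts at zero and grows in a straight line to half an SD at the final visit. A large effect is named but not defined. The other inputs are attrition of 10% and 20% and correlations of .2, .5 and .8. The conclusion is that "the proposed total sample size of at least 48/arm" "would be sufficient to achieve a minimum 80% power for the primary aim". The paragraph gives no significance level and does not separate hypothesis 1a from 1b.

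Table 1 labels CAPS-5 as Aim 1a and five scales as Aim 1b: depression (CESD-R), anxiety (STAI), anger (STAXI-II), insomnia (ISI) and disability (SDS).

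The mixed-model paragraph of the Analytic Plan sets the decision rules: "Statistical significance will be determined by $p < .05$ for hypothesis 1a", and p < .01 for 1b, the divisor being given as "05/5 to correct for multiple comparisons) for hypothesis 1b". It is also stated that "All statistical tests will be two-tailed".

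**The concern.** Five of the six Aim 1 outcomes are judged by a stricter rule that the power paragraph never mentions. The 80% is therefore not tied to the test that will be carried out on those five. A reader who takes Aim 1 as Table 1 defines it would credit the trial with at least 80% power for depression, anxiety, anger, sleep and disability. If the true figure is much lower, a non-significant 1b result carries far less information than the stated power suggests. The figure also justifies the reduced sample of about 96.

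**Working it through.** **Inputs from the documents.** 48 per arm (Sample size; Procedures says that "the allocation will be reversed to 1:3 for the final months of the study to accomplish a minimum of 48/cell"); medium effect 0.5 SD at the last visit; attrition 10% and 20%; r = .2, .5, .8; two-sided alpha .05 (1a) and .01 (1b). Table 1 gives at least four assessments (baseline, mid-treatment, post-treatment, follow-up) for the 1b scales and three for CAPS-5, which has no mid-treatment visit.

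**Assumptions, not in the documents.** Large = 0.8 SD; equally spaced visits; compound symmetry; dropout reached steadily by the last visit (retention 1/.967/.933/.90 or 1/.933/.867/.80 for four visits; 1/.95/.90 or 1/.90/.80 for three).

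**Formula.** The test is the group difference in linear slope, by generalised least squares. With outcome SD 1, visit times 0 to T and no dropout, the standard error of the last-visit difference implied by the slope is

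SE = T × √[2(1 − r) / (n × Sxx)].

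For four visits T = 3 and Sxx = 5, so at r = .5, SE = 3 × √[2 × 0.5 / (48 × 5)] = 0.194. With dropout, the information in each arm is summed over dropout patterns, n × Σ p_k X_k′V_k⁻¹X_k. At 10% / 20% attrition this gives SE = 0.253 / 0.262 (r = .2), 0.201 / 0.209 (r = .5) and 0.128 / 0.134 (r = .8).

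Power is the upper tail of a noncentral t with λ = δ/SE on 96 − 2 = 94 df, beyond 1.986 (alpha .05) or 2.629 (alpha .01). Example: δ = 0.5, r = .5, 10% attrition gives λ = 0.5/0.201 = 2.49, hence 69% at .05 and 45% at .01.

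**Results, four visits (20% to 10% attrition).**

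| Effect | r | Power at .05 | Power at .01 | Fall (points) |
|---|---|---|---|---|
| 0.5 SD | .2 | 47–50% | 24–26% | 23–24 |
| 0.5 SD | .5 | 66–69% | 41–45% | about 25 |
| 0.5 SD | .8 | 96–97% | 86–90% | 7–10 |
| 0.8 SD | .2 | 86–88% | 66–70% | 18–19 |
| 0.8 SD | .5 | 97–98% | 88–91% | 7–9 |
| 0.8 SD | .8 | about 100% | about 100% | 0 |

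**The plan's own figure.** At .05, the 80% minimum is reproduced for the large effect throughout and for the medium effect at r = .8. It is not reproduced for the medium effect at r = .2 or .5. Over the 12 cells (two effects, three correlations, two attrition rates), 8 reach 80% at .05 and 6 at .01. The two that change are the large effect at r = .2.

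**Hypothesis 1a on its own design.** CAPS-5 with three visits at .05 has SE 0.266 / 0.276, 0.212 / 0.221 and 0.135 / 0.141. Power for 0.5 SD is about 43–46% (r = .2), 61–65% (r = .5) and 94–96% (r = .8).

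**Smallest difference with 80% power.** This is approximately (critical t + 0.846) × SE.
- 1b at .01: 3.475 × SE = 0.88–0.91 SD (r = .2), 0.70–0.73 (r = .5), 0.44–0.46 (r = .8).
- 1a at .05: 2.832 × SE = 0.75–0.78 SD, 0.60–0.63 and 0.38–0.40.

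**Sensitivity, large effect at r = .2, alpha .01.** A normal approximation gives 69–73%. Over other compound-symmetry attrition patterns, spacings and contrasts the range is 50–76%. AR(1) correlation with 10–20% total attrition gives about 54–57%. A model that forces equal baselines would give 90–96%, but the Analytic Plan specifies a fixed group effect plus group-by-time, which does not impose that constraint.

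**The case against.** The strongest reply is that a power statement for the primary aim normally means the primary outcome. The Clinical outcomes section makes the CAPS total the primary measure, and the Background summary treats associated symptoms as a secondary assessment. A reader might infer that the plan promises 80% for each 1b outcome; it never says so. This stands as a possible reading. Against it, the same paragraph says that the sizing was for Aim 1, and Table 1 puts 1b inside Aim 1. Under the CAPS-only reading, the text still needs to name the outcome and alpha.

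A second reply is that most of the shortfall is not caused by the .01 threshold. That is right. A reader might infer that the threshold costs 18–25 points everywhere, but that holds in half of the grid only; elsewhere the fall is 0–10 points. Only for the large effect at r = .2 does the alpha alone move power from above 80% to below it.

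Third, lower power for secondary outcomes is the ordinary price of a Bonferroni correction, and the plan states the correction openly. That is also fair: the threshold is not at fault, only the power figure that ignores it. Nor does the plan say that a non-significant 1b result will be read as no effect, so that misuse is a risk for readers and not a stated intention.

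Fourth, four visits do not fit every scale exactly: Table 1 has only the state part of the STAI at mid-treatment and has the CESD-R weekly as well. The figures are therefore approximate by outcome.

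**Conclusion.** The concern holds in a limited form. The 80% minimum is stated for Aim 1, or the primary aim, with no alpha or outcome, and it is not delivered for the 1b outcomes at the .01 threshold across the plan's own grid. Per-outcome power for the medium effect is about 24–45% at r = .2 to .5 and passes 80% only near r = .8. For an assumed large effect of 0.8 SD it is 66–70% at r = .2 and above 80% at r = .5 and .8. These figures rest on 48 per arm, four equally spaced visits, compound symmetry and 10–20% monotone attrition. Another covariance, attrition pattern or baseline treatment would move them as shown.

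The documents do not support the inference that 80% would be right if it were confined to 1a. On the stated medium effect at r = .2 and .5, CAPS-5 also falls short at .05.

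**What to change.** In the Sample size paragraph, replace the blanket 80% with power stated by hypothesis.

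- **1a:** CAPS-5, three visits, alpha .05. Give the effect size and correlation at which 80% is actually reached. Do not simply attach the existing 80% to this hypothesis.
- **1b:** alpha .01 per outcome. Give either the power over the same grid or the smallest difference detectable with 80% power (about 0.9 SD at r = .2, 0.7 SD at r = .5 and 0.45 SD at r = .8 under the assumptions above). Alternatively, say that 1b does not have 80% power for the medium effect unless correlations are near .8.
- **Both:** define the large effect, and state the correlation structure and attrition pattern used.

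The cost is one recalculation and revised wording. The stated power becomes less favourable. Patients, visits and tests are unchanged.

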Thus, the successful track record of implementing clinical and research programs using complementary approaches at the VASDHS, is strong evidence for the acceptability of this type of study at this facility.

Feasibility

Although we initially projected being able to enroll approximately 6 Veterans per month in the trial for a sample of 144 completers, this has not proven to be realistic. In 38 months of active recruitment, we have screened 326 individuals (~9/month) of whom 51% consented to participation and 26% were randomized (~2.5/month). We believe that these lower-than expected rates of participation and randomization are partly related to competition with many other opportunities to engage in recorded or live-streamed yoga/exercise classes. As a result, we plan to enroll approximately 96 Veterans in the trial (48/group).

Pilot Effect Sizes

Effect sizes in studies of yoga for PTSD vary widely (0.08 to 1.65; Wells, [name], Schmalzl, Groessl, & Strauss, 2016), perhaps because of variability in practice types and the populations studied. The largest randomized controlled trial of yoga for PTSD to date compared a “trauma sensitive” version of Kundalini yoga to a wait list control in an 80-person civilian sample (Jindani et al., 2015). Greater decreases in PTSD symptoms (Cohen’s $d = 1.65$), insomnia, stress and anxiety were observed in the yoga group. In addition, yoga was associated with increased in positive affect and resilience. No significant changes in depression or negative affect were observed. This trial is limited, however, by the lack of an active control and a high rate of

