of clinical utility will be assessed by examining recruitment/retention data and feedback from referring clinicians and Veterans in preparation for future implementation of practice guidelines.

Mechanisms of change: Attention model. The **Philadelphia Mindfulness Scale (PMS;** Cardaciotto, [name], Forman, Moitra, & Farrow, 2008) is a 21-item measure that assesses present-moment awareness and acceptance and has good internal consistency (Cronbach's α .75) and validity (e.g., corresponds highly with other measures of mindfulness but not with measures of psychopathology or social desirability) in psychiatric samples.

To fully characterize the nature of yoga's impact on attention, we will utilize multi-modal assessment including two tasks with an affectively neutral context, as well as two tasks that include affective stimuli to allow for an assessment of the ability to deploy attentional resources in emotional contexts. The **Digit Span** test from the Wechsler Adult Intelligence Scale 4th edition (WAIS-IV) will be used as a standardized neuropsychological measure of attention and working memory (Wechsler, Coalson, & Raiford, 2008). This test includes Digit Span Forward, wherein the participant is read a sequence of numbers and recites the numbers back in the same order; Digit Span Backwards, wherein the participant is read a sequence of numbers and must recite them back in reverse order; and Digit Span Sequencing, wherein the participant is read a sequence of numbers and must recite them back in numerically ascending order. Digit Span is a well validated assessment with established norms, and has been shown to be sensitive to change in a study using a yoga intervention (Brunner et al., 2017). Each subtest is scored based on the number of items correctly recited on each trial.

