conditioning. Each exercise can be modified to meet the needs of individual participants. The classes will be conducted by certified personal trainers. This control group was selected because of its past use as a control condition for Hatha yoga. This type of exercise program was comparable to Hatha yoga in terms of gains in functional fitness (Gothe & McAuley, 2016) but less effective at improving cognition (Gothe, Kramer, & McAuley, 2014) in community-dwelling samples of older adults.

Analytic Plan

Descriptive statistics will be obtained for all variables, including distributions, means, medians, variances, standard deviations, skewness, kurtosis, ranges, and quartiles. Tests of normality of continuous measures will be made using the Shapiro-Wilk W and the Kolomogorov D statistics in conjunction with plots of the distribution of data and descriptive measurements. The data will also be examined for homogeneity of variance. An appropriate statistical method will be employed to correct for any abnormalities. Missing data values will be minimized by intensive training of the assessors in techniques of clarifying answers and checking questionnaires while participants are on-site. When missing values are identified, we will employ several approaches to reduce their influences. If at all possible, participants will be rescheduled or a telephone call will be made within 24 hours of completion of tests or interviews. The pattern of missing data will be examined according to the procedure recommended by Little and Rubin (1987), which includes comparing group differences in the primary outcomes of subjects with versus without missing data. We will also test whether the drop-outs are random or systematic by comparing the drop-outs with the study completers on the baseline data. An absence of significant differences would support the random nature of drop-outs. Effect of drop-outs will be minimized by including all subjects in the analyses and by including any effect of systematic differences between the drop-outs and completers in the model as a covariate when applicable.

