Hiring					
Training					
Revised Timeline 2022					

 ✓ Set-up ✓ Regulatory 	
 In person recruitment → Transition → Remote recruitment Assessment Intervention delivery, fidelity Data management, including QA/QC and data lock DMC reporting 			Analyses, Dissemination	
Hiring					
Training					

Data Management

Data management and statistical analysis will be supervised by [name]. [name] is a biostatistician at the VASDHS and an Assistant Adjunct Professor in the UCSD Department of Family Medicine and Public Health. She has prior experience in VA clinical trials, including studies of yoga and PTSD, and has previously collaborated with [name]. [name] will oversee the development of the study database, which allows for automated data validation and auditing. Data will be maintained on the secure VA research server. Participant names will be held separate from data. Subjects will be assigned a unique ID number, and the single name-to-ID relational file will be kept in an encrypted form electronically and in a locked filing cabinet physically. Statistical analysis will be conducted using SPSS, R and SAS software packages. All statistical transfer routines are inherently secure via their operating platform and they contain no patient names or personal data.

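### Recruitment went remote and allocation moved from 2:1 to 1:3, but no model carries enrolment mode or allocation phase, so a mode or era effect on CAPS change would leak modestly into the arm contrast

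*Combined protocol and SAP*

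**What the plan says.** Four parts of the combined protocol and SAP bear on this.

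- **Table 2, Revised Timeline 2022.** Recruitment is shown as "In person recruitment → Transition → Remote recruitment". Assessment and intervention delivery are listed with no mode, and no dates or head counts are given.
- **Procedures, randomization paragraph.** In the initial phase "this was a 2:1 allocation to yoga and physical activity and took place at the individual level". Because of slow accrual, "the allocation will be reversed to 1:3 for the final months of the study to accomplish a minimum of 48/cell". I read 1:3 as yoga to physical activity, since it is described as a reversal.
- **Analytic Plan, hypotheses 1a and 1b.** The model has a random intercept, a random time effect and "fixed effects for comparison groups and group-by-time interaction in the model". The only possible additions are a group-level random effect kept or dropped by AIC and covariates that separate drop-outs from completers. The mediation analysis for Aim 2 adds no mode, calendar-period or phase term, and no sensitivity analysis addresses them.
- **Analytic Plan, missing data, and Clinical utility.** Missing answers are to be limited by "clarifying answers and checking questionnaires while participants are on-site", with rescheduling or a telephone call within 24 hours as a second safeguard. Aspects "of clinical utility will be assessed by examining recruitment/retention data", with no split by mode or phase.

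**The concern.** A change of recruitment mode under a constant allocation ratio is harmless to the arm comparison in expectation, because both arms receive the same mixture. A change of ratio makes phase a confounder unless the analysis conditions on it. Here both changes happened, in a known order: in-person recruitment and 2:1 allocation came first, remote recruitment and 1:3 allocation come last. In-person recruits therefore entered while two of every three went to yoga, and the last recruits enter while three of every four go to physical activity.

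If people recruited in person and remotely differ in how much their CAPS score changes, or if anything else that drifts over calendar time does so, part of that difference will appear as a yoga effect or will mask one. The sign is unknown. Retention compared by arm has the same weakness.

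**Working it through.** **Accrual figures (Feasibility).** 26% of 326 screened is 0.26 × 326 ≈ 85 randomized. The stated rate of about 2.5 per month over 38 months would give 95; 85/38 is 2.2 per month. I use 85. The ratio change is written in the future tense, so I take all 85 as allocated 2:1.

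**Arm sizes.**
- 85 at 2:1: 56.7 yoga, 28.3 physical activity.
- To reach 48 controls at 1:3: (48 − 28.3)/0.75 ≈ 26 more, of whom about 6.6 go to yoga. Final size about 63/48.
- If enrolment stops at 96: 11 more, split 2.75/8.25. Final size about 59.4/36.6.

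**Assumptions not in the documents.** f is the share of 2:1 participants recruited in person, taken as 20–70%. δ is the effect of mode on CAPS *change*, taken as 0.3–0.5 SD. The 1:3 phase is taken as wholly remote.

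**Formulas.** In-person share of an arm = f × (arm size in the 2:1 phase)/(final arm size). Bias = (yoga share − control share) × δ.

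Final 63/48: the multipliers are 56.7/63.2 = 0.896 and 28.3/48 = 0.590, a gap of 0.306f.

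| f | Yoga in person | Control in person | Bias, δ = 0.3 | Bias, δ = 0.5 |
|---|---|---|---|---|
| 20% | 18% | 12% | 0.018 SD | 0.031 SD |
| 50% | 45% | 30% | 0.046 SD | 0.077 SD |
| 70% | 63% | 41% | 0.064 SD | 0.107 SD |

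Stopping at 96: 56.7/59.4 − 28.3/36.6 gives a gap of about 0.18f. Bias runs from 0.18 × 0.2 × 0.3 ≈ 0.01 SD to 0.18 × 0.7 × 0.5 ≈ 0.06 SD. Starting from 95 at 2:1 gives a gap of 0.261f, so the bias stays within the 63/48 range.

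**Check by simulation** (85 at 2:1, 26 at 1:3, δ = 0.5 SD). Unadjusted bias was 0.03, 0.08 and 0.11 SD at f = 20%, 50% and 70%, matching the table. A phase indicator alone brought it to zero within simulation error. So did a recruitment-mode covariate alone, with almost no loss of precision.

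**Price of adjusting for phase.** Information is the sum over strata of n_Y·n_P/(n_Y + n_P).
- 63/48: pooled 27.3, within phase 23.8, ratio 0.872. The standard error rises by 1/√0.872 = 1.07 if the covariates explain no variance; in simulation with a 0.5 SD mode effect the rise was about 5–6%.
- Most extreme 96-participant case, 48/48 with 57.6 at 2:1 (38.4/19.2) and 38.4 at 1:3 (9.6/28.8): pooled 24, within phase 20, a loss of about 17%. This does not fit about 85 already allocated at 2:1, so it is an outer bound.

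**The case against.** **Only recruitment is labelled remote.** A reader might infer that classes and assessments moved too, and that two differently measured eras are being pooled. There is some support: the recruiter is also the assessor, and the CAPS-5 both establishes the diagnosis and serves as the primary outcome. But the timeline gives no mode for assessment or delivery, and the missing-data text still describes on-site visits. The inference is not established. Nor does the on-site check stand alone, since the telephone safeguard does not depend on attendance in person.

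**The imbalance is the ratio change.** This is right. Within a phase of constant ratio, mode is independent of arm in expectation, so a phase term alone removes the bias in the arm contrast. Mode earns its place as a cheap pre-randomization covariate, for Aim 2, and for describing whom the results apply to.

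**A level shift cancels.** If mode merely moves all of a participant's scores up or down equally, group-by-time is unaffected. The bias needs an effect on change, which is assumed here.

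**Aim 2 false positives.** A reader might expect serious inflation if mode shifts mediator and CAPS together. Rejection rates of 21–27% at a nominal 5% require 30–50% of participants to be shifted by 0.8 SD. At about 2.5 enrolments per month, a sharp switch would catch about 8 of 96 between baseline and week 14 and about 15 by follow-up. With 8–16% shifted, rejection is about 5–6% at 0.3–0.5 SD and about 8–12% at 0.8 SD. A long transition would raise these figures, but its length is not given. The plan already says that the mediation method may not be supportable at the reduced sample size.

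**Conclusion.** The concern holds in a limited form. The order of events in the documents implies more in-person recruits in the yoga arm, and nothing in the planned models absorbs a mode or era effect. A zero gap would need the whole 2:1 phase to have been remote, which that order contradicts.

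The size is modest: about 0.02–0.11 SD if allocation runs on to 48 controls, and about 0.01–0.06 SD at 96, against a design effect of 0.5 SD. For scale, with three CAPS visits and a correlation of 0.5, a bias of 0.077 SD raises a 5% two-sided test to about 6.9%. All of this rests on assumed values for f and δ and on taking the first 85 as allocated 2:1.

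A larger bias, such as 0.20 SD, would need only about 58 participants at 2:1, all in person, and a 0.5 SD mode effect; the accrual figures do not fit that. The documents do not show that outcome measurement changed. The plan as written is slightly worse than one with a small, inexpensive addition to the model.

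**What to change.** 1. **Analytic Plan, hypotheses 1a and 1b.** Add two baseline terms to the CAPS and 1b models, each with its interaction with time: mode at enrolment (in person or remote, fixed before randomization) and allocation phase (2:1 or 1:3). If the two coincide completely, keep phase.
2. **Analytic Plan, mediation.** Add the same baseline covariates to the mediator and outcome equations.
3. **Procedures or Table 2.** State the dates of the recruitment switch and the ratio change, and the mode of classes and assessments in each period. If assessments also changed mode, add mode at the visit as a sensitivity analysis only, because few participants would inform it.
4. **Reporting.** Give effects, retention and missingness by enrolment mode within arm, descriptively. Do not adjust for or stratify by the mode of the classes attended: that depends on how long someone stayed, which is settled after randomization.

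**Cost.** With three CAPS visits and time as a factor, each two-level covariate uses 1 + 2 = 3 degrees of freedom, so 6 in all. The standard error rises by about 5–7% at 63/48, with 17% of information as the outer bound at 96. For a 0.5 SD effect at 63/48, correlation 0.5 and no attrition, phase adjustment lowers power from about 74% to 68%. Mode-specific estimates will be imprecise. The enrolment-mode flag must be coded from study records, assuming they hold it.
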